### **Primary outcome measures**

The primary outcome measure, focused on achievement of the PACT model of care for WVs, will include changes in levels of achievement of individual PACT features: access, continuity, care coordination, team-based care, patient-driven care, patient-centeredness, comprehensiveness (including gender-specific services and integrated MH), and gender sensitivity (Fig. 2). These measures will be examined at the practice, provider/ staff, and patient levels and investigated qualitatively using the key stakeholder and teamlet interviews.

### **Secondary outcome measures**

Secondary outcome measures include WH-PACT outcomes that should result from achievement of the full PACT model, including improvements in quality of care and health status, and reductions in utilization and costs. For quality of care, we will examine chronic disease quality (e.g., process measures such as foot sensation exams or eye exams among diabetics) and preventive practice (e.g., women's breast and cervical cancer screening and gender-neutral prevention, such as influenza immunizations and colorectal cancer screening). We will determine whether total annual costs per patient and utilization by type of care (e.g., primary care, specialty care, hospitalizations, emergency department visit rates) have changed in EBQI vs. routine PACT implementation VAMCs and based on level of WH-PACT achievement. We anticipate, however, that acute and emergency care may be too rare in our practice populations to have the power to detect differences over time, so these analyses will be exploratory.

We will also examine impacts on provider and staff WH knowledge and attitudes, QI orientation/culture, and gender awareness, as well as changes in practice contextual factors as a result of EBQI exposure (e.g., changes in leadership support, local resources applied to WH and primary care QI, training).

### **Statistical analyses**

We will use multivariate regression to determine EBQI effectiveness, adjusting for covariates, clustering, and enrollment and attrition weights at the patient and provider/staff levels. The primary regressor of interest is being at an EBQI vs. routine PACT implementation site. We will examine the potential moderating effects of practice context and provider/staff knowledge/attitudes. Patient-level controls will include sociodemographic characteristics, health status, comorbidity, and utilization. Adjustment for clustering will be performed using Stata v13. We will evaluate goodness-of-fit using Mallows's statistic ( $C_p$ ). We will use multiple imputation methods to address missing data patterns among covariates, although CATI procedures will significantly reduce item non-response in the patient survey, and the web-survey methods will do the same for the provider/staff surveys. Hot deck imputation will be used for imputation of missing values within scales as needed. To address the potential for response bias, patient and provider/staff survey data will be weighted to the inverse of the probability of selection based on available characteristics in the administrative data used to randomly sample them. We will use factor analysis and cluster analysis using PACT features (e.g., access), comprehensive women's health care (e.g., gender-specific care availability), and gender-sensitive care delivery (e.g., availability of same-gender providers or gender-aware providers) for WH-PACT achievement variable creation.

All semi-structured interviews will be audio-recorded and transcribed, and qualitative analysis will be conducted using ATLAS.ti version 7. Interview domains are noted in Table 2.

[figure not shown]
Initially, a top-level codebook will be developed for the baseline interviews based on the interview guide. The codebook will then be elaborated based on emergent themes using a constant comparison analytic approach, adjusting as each round of interviews is reviewed. Interviews will be compared within and across facilities and over time. In baseline key stakeholder and teamlet transcripts, we will conduct targeted coding of PACT-related knowledge, attitudes, beliefs, and experiences; expectations of WH-PACT's effectiveness; and practice contextual factors that influence how care is delivered (and changed) locally. In follow-up key stakeholder transcripts, we will identify factors that facilitated and/or impeded EBQI and WH-PACT achievement and strengths/ weaknesses of the WH-PACT model as implemented.

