## **Methods/design**

### **Setting, site selection, trial design, and participants**

The VA healthcare system is currently organized into 21 regional Veterans Integrated Service Networks (VISNs), with administrative and clinical authority over VA medical centers (VAMCs) and their affiliated programs in geographically distinct regions of the USA [16]. Study sites are members of the VA Women's Health Practice-Based Research Network (WH-PBRN), a 37-VAMC network spanning 17 VISNs and comprising over 270 geographically distinct sites of care and nearly 600 designated WH providers [17]. Together, PBRN facilities serve over 100,000 WVs (about one third of WVs seen in VA) and span diverse patient populations. We identified five VISNs with three or more WH-PBRN sites; we excluded one that was already participating in a VISN-wide EBQI stepped-wedge trial. We approached leadership at the other four VISNs and their WH-PBRN member site leads about study participation. All agreed to participate. One VISN dropped out ahead of randomization, which was replaced with a VISN that had two WH-PBRN sites; we then worked with VISN leadership to identify a third non-PBRN VAMC, which subsequently joined the WH-PBRN (since the trial began, the WH-PBRN has expanded to 60 VAMCs in 20 of 21 VISNs). VAMCs participating in the trial span nine states (Connecticut, Illinois, Iowa, Massachusetts, Minnesota, North Dakota, Pennsylvania, West Virginia, and Wisconsin).

This study is designed as a parallel two-arm, cluster randomized controlled trial (cRCT), blocked on VISN (Fig. 1). We randomly assigned the 12 VAMCs to EBQI or usual PACT implementation in an unbalanced 2:1 ratio within VISN, supporting appraisal of variations in EBQI implementation in the context of differences of VISN geography, resources, and oversight (Fig. 1). No site stratification or matching criteria were used. The study biostatistician used [www.randomization.com](http://www.randomization.com) with a randomized permuted block of three (simple block of three

VAMCs within each VISN) and a seed of 15,356 to start the random allocation sequence. The eight intervention VAMCs will engage in EBQI, while the four control VAMCs will receive standard PACT and WH care delivery handbooks and guidance that all VA facilities receive. The study biostatistician assigned the VAMCs to EBQI or control, while the study PI ([name]) enrolled and launched EBQI with the resulting eight VAMCs.

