## **Sample size calculation and power analysis**

We based our power calculations on the study’s unequal (2:1) intervention-to-control ratio and clustered sample design. To detect a moderate (0.20) effect size between WVs at intervention and control sites, we considered data from the Primary Care Satisfaction Survey for Women’s Care Coordination and Comprehensiveness scale, [33] with 12 practices (8 intervention-to-4 control sites), cluster adjustment ( $ICC = 0.03$ ) [34], and two-tailed 5 % significance level. Based on these parameters, we will target enrollment of a minimum of 40 WVs at each of the 12 study sites over the 2-year period (baseline to 24-month follow-up), for a total of 480 WVs who complete a baseline and at least one of the two follow-up surveys (12- and/or 24-month). To achieve this target, we will create a baseline sample of 6665 WVs who have received PC or WH care at one of the study’s 12 participating sites during the 12-month period prior to the baseline survey (555 per site). Allowing for a conservative 20 % response rate and 40 % attrition over the 2-year period, we aim to enroll 111 WVs at each of the 12 sites at baseline, for a total of 1333 interviews at the completion of the first wave.

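### The analysis names neither the VISN blocks nor a small-sample method for 12 sites (8 vs 4), so ordinary clustering inference can miss the 5% level and an unblocked test can lose power

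*Combined protocol and SAP*

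**What the plan says.** The design section describes a "cluster randomized controlled trial (cRCT), blocked on VISN" and reports that "We randomly assigned the 12 VAMCs to EBQI or usual PACT implementation in an unbalanced 2:1 ratio within VISN". Each of the four VISNs therefore holds two EBQI sites and one control site. The power section works with "12 practices (8 intervention-to-4 control sites"), an ICC of 0.03, at least 40 patients per site and a "two-tailed 5 % significance level".

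The Statistical analyses section plans a regression of outcome on study arm, "adjusting for covariates, clustering, and enrollment and attrition weights at the patient and provider/staff levels". The only controls it lists are at patient level: "Patient-level controls will include sociodemographic characteristics, health status, comorbidity, and utilization". On the method for clustering it says "Adjustment for clustering will be performed using Stata v13". On missing data it says "We will use multiple imputation methods to address missing data patterns among covariates". Nowhere do the documents name an estimator, a reference distribution, degrees of freedom, a small-sample correction or a randomization test, and nowhere is VISN put in the outcome model.

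**The concern.** The sentence on clustering names software, not a method. Stata offers several ways to handle clusters, and with only 12 sites, four of them control, these do not share the same true error rate. Standard cluster-robust and mixed-model inference relies on many clusters.

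The two gaps pull in different directions. Having no small-sample method tends to push the level up. Leaving out the block tends to push it down and waste power, because VISN differences remain in the residual variance although the design has already balanced them out of the comparison. The net level then depends on an unnamed method and an unknown VISN variance. With so few sites, the choice of method can decide whether a result is called significant.

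**Working it through.** **Inputs from the documents:** 12 sites, 8 vs 4, in four VISNs of three (design section); 40 completers per site, ICC 0.03, two-sided 5%, effect 0.20 (power section).

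**Assumptions:** total variance 1, so that 0.20 is in SD units (the plan does not define the metric); equal site sizes; a share s of the between-site variance lying between VISNs, taken as 0, 25 or 50%; and the estimator.

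**1. The plan's own figure.** 12 × 40 = 480 reproduces. No target power is stated, so the calculation behind it cannot be checked further. The design effect is 1 + 39 × 0.03 = 2.17. The variance of a site mean is 2.17/40 = 0.05425, which equals 0.03 + 0.97/40.

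**2. Why default cluster-robust errors run high** (s = 0, site-mean variance V). The true variance of the arm difference is V(1/8 + 1/4) = 24V/64.
- Arm only: squared residuals average 7/8 of V in the EBQI arm and 3/4 of V in the control arm. The robust variance averages V[(7/8)/8 + (3/4)/4] = 19V/64. With the usual 12/11 factor this is (19/24)(12/11) = 0.86 of the truth.
- VISN terms added: the arm indicator centered within VISN is 1/3 (EBQI) or −2/3 (control), with sum of squares 8/3. Leverages are 3/8 and 1/2. The robust variance averages V[8(1/9)(5/8) + 4(4/9)(1/2)]/(8/3)² = 13V/64. With the factor this is (13/24)(12/11) = 0.59 of the truth. VISN terms alone make default robust inference worse.

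**3. Why leaving VISN out is conservative.** Each VISN contributes two EBQI sites and one control, so VISN effects cancel from the arm difference. Its true variance is 0.375 × [0.03(1 − s) + 0.97/40]. The unblocked residual variance on 10 df averages the bracketed term plus 0.9 × 0.03s, because the VISN part of the sum of squares is 6 in the EBQI arm and 3 in the control arm, over 10.
- s = 25%: (0.04675 + 0.00675)/0.04675 = 1.14 times too large.
- s = 50%: (0.03925 + 0.0135)/0.03925 = 1.34 times too large.

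**4. Simulated type I error at nominal 5%** (40,000 trials; allocation drawn from the 81 possible within-VISN allocations; simulation SE about 0.1 point):

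| Method | s = 0 | 25% | 50% |
|---|---|---|---|
| No VISN, cluster-robust t(11) | 7.9 | 6.2 | 5.0 |
| No VISN, cluster-robust z | 11.1 | 9.1 | 7.3 |
| No VISN, random intercept REML, z | 7.5 | 5.7 | 4.3 |
| No VISN, random intercept ML, z | 9.5 | 7.5 | 5.8 |
| No VISN, site-level t(10) | 5.1 | 3.8 | 3.0 |
| VISN, cluster-robust t(11) | 14.4 | 14.2 | 14.5 |
| VISN, random intercept REML, z | 8.1 | 7.4 | 6.8 |
| VISN, site-level t(7) | 5.1 | 4.8 | 5.1 |
| VISN, within-VISN permutation | 5.1 | 4.8 | 5.1 |

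With site sizes from 20 to 60 (total 480), the t(7) test gives 4.8 to 5.0%. With an assumed 15 providers or staff per site and ICC 0.03 or 0.10, it gives 4.7 to 5.2%, against 7.7% for robust t(11) at s = 0.

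**5. Power at 0.20 SD, ICC 0.03.** The blocked test has 12 − 4 − 1 = 7 df. Its noncentrality is 0.20/√(0.375 × 0.05425) = 1.40 at s = 0, 0.20/√(0.375 × 0.04675) = 1.51 at 25%, and 0.20/√(0.375 × 0.03925) = 1.65 at 50%.

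| Test | s = 0 | 25% | 50% |
|---|---|---|---|
| No VISN, t(10) | 24.5 | 23.8 | 23.1 |
| VISN, t(7) | 22.9 | 25.8 | 29.7 |

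At s = 10% the two are close (24.3 vs 23.9%). At ICC 0.01, t(10) against t(7) gives 35.8 vs 33.1% (s = 0), 35.2 vs 34.6% (25%) and 35.4 vs 37.5% (50%). If 0.20 stood for 0.40 SD, the ICC 0.03 figures would be 71 vs 67%, 73 vs 74% and 75 vs 81%.

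**The case against.** The documents are silent rather than wrong. Covariates are mentioned without a closed list, so VISN may be intended; a reader might infer that the plan excludes VISN, and the text does not show that.

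A reader might also infer that the planned test runs above 5%. That does not follow either. The estimator is unknown, and if half the between-site variance lies between VISNs, robust t(11) without VISN sits at about 5% and REML with z at 4.3%. Nor does omitting VISN itself inflate the level; it does the opposite. The site-level t(10) test does not materially exceed 5% in these runs, so VISN is not needed for validity. Its case is power, and that rests on shares the documents do not give. The 5% level itself is printed only in a power calculation for one patient scale.

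All of this stands and limits the point. It does not remove it. The sponsor cannot count on an offset from a VISN variance that nobody has stated, and if VISN is intended as an ordinary covariate with default robust errors, the level is at its worst.

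**Conclusion.** The point holds in conditional form. The plan fixes neither the block term nor a small-sample method, and methods compatible with its wording have true levels from about 3% to about 14% at a nominal 5%. Of the approaches simulated, the two that combine VISN with small-sample inference stayed close to 5% at every share tried.

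Against the unblocked t(10) test, the power effect of adding VISN runs from a loss of about 2 points (ICC 0.03) or 3 points (ICC 0.01) when VISNs do not differ, to a gain of 6 to 7 points at ICC 0.03 with a 50% share. Break-even is near a 10% share at ICC 0.03, and near or somewhat above 25% at ICC 0.01.

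The figures rest on the assumed estimators, VISN shares and SD metric. Practice-level outcomes, non-normal scales and weights correlated with outcome were not simulated. How the 12- and 24-month waves are used is a separate matter.

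**What to change.** This is a cheap improvement: SAP wording and a short program, with no change to design or data. State, before the arms are compared on follow-up data, that the EBQI comparison for patient and provider/staff survey outcomes includes VISN as the randomization block together with a small-sample method suited to 12 sites. One example:

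- Stage 1: regress the follow-up value on its baseline value (where collected), the individual-level covariates and VISN, with the planned weights and without arm. Take each site's weighted mean residual.
- Stage 2: regress the 12 site values on arm and VISN. Take the estimate, 95% CI and p-value from this model on 7 df.

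With a baseline term (assumed correlation 0.5) and weights (assumed CV 0.5), this example ran at 4.7 to 5.1% in 8,000 simulated trials. Other methods shown to hold 5% would also do.

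With multiple imputation, pool the estimate and its variance by Rubin's rules on no more than 7 df. This is slightly conservative: 4.0 to 4.3% with 20% of one covariate missing and 10 imputations. A within-VISN permutation test over the 3⁴ = 81 allocations can serve as a check (smallest p = 1/81 = 0.012). Apply it to site values averaged over imputations, since permutation p-values cannot be pooled by Rubin's rules.

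Do not add VISN terms alone with default cluster-robust or z inference.

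The cost is 7 rather than 10 df, with the small power loss given above if VISNs barely differ. Each site-level covariate costs one further df.

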### **Trial timeframe**

The WH-PACT trial is planned from March 2013 through February 2017 (Fig. 1). Phase 1 network-level stakeholder panel meetings occurred as half-day in-person meetings from May to August 2014. Phase 2 local QI launched at all eight EBQI-assigned VAMCs in October 2014. Baseline key stakeholder interviews in all participating VISN and VAMC followed within days of each respective network-level meeting, followed by teamlet interviews at EBQI sites only within one quarter of each meeting. Provider and staff surveys were fielded to PC and WH providers and staff in all participating VAMCs starting September 2014, while baseline patient surveys were launched in January 2015, yielding formative feedback in the following year. EBQI will run for 24 months from launch of local QI teams, followed by 24-month follow-up interview and survey waves.

**Figure 1:** Consort flow diagram for cluster randomized controlled trial of evidence-based quality improvement

[figure not shown]

**Table 1:** Core components of evidence-based quality improvement (EBQI) implementation strategy

EBQI component	Activities	Example product(s)

Conduct of VISN-level interdisciplinary stakeholder planning meetings to develop “QI roadmaps”
	
Modified Delphi panel meetings with materials on PACT and panel ratings in advance of an in-person presentation of aggregated pre-panel ratings for review and moderated discussion and consensus development on top priorities for QI in context of feasibility of implementation and local resources
	
Panel materials
 
 
• Panel rating form
 
• Summary of women Veterans’ research
 
• VISN-level gender differences in patient ratings of care
 
• Local practice and patient population characteristics
 
 
VISN-level QI roadmaps
 
 
• Brief panel presentation summary
 
• Brief summary of top VISN priorities for QI for PACT for women Veterans
 
• Brief summary of top-rated topics requiring technical support (e.g., care coordination between VA and non-VA providers)
 
• Oversight and communication plans
 


Development, training, and support of local QI champions and QI team members
	
In-person training of 1–2 local QI champions at the parent study site in Los Angeles
 
 
• National PC and WH leadership endorsement
 
• Review VISN QI roadmaps and planned QI projects across intervention sites
 
• Review approaches to QI
 
• Breakout groups on applying QI methods/tools to project plans
 
• Across-team debriefing
 
• Formative feedback from key stakeholder interviews
 
• Breakout groups on applying EBQI principles to WH-PACT QI projects
 
• Training on EBQI formative feedback reports and Technical Work Groups
 
• Exemplar session on using EBQI to improve PACT team functioning
 
• Q&A panel with EBQI experts
 
	
Training materials (reader, slidesets, breakout exercises, in-person expert EBQI project consultations)
 
Follow-up technical consults on local QI plans (with QI/system redesign consultant by email/phone)

	
on lessons learned from prior projects
 
 
• Training on local QI project documentation
 
	
Formative feedback of local QI data	
 
• Feedback of baseline and 12-month survey data from women Veterans seen in participating VAMC primary care clinics
 
• Feedback of baseline PACT provider and staff survey findings
 
• Feedback of key themes from baseline interviews of VISN, VAMC and practice-level key stakeholders
 
• Feedback of key themes from baseline interviews of PACT teamlet members in participating VAMCs
 
• Feedback of VA quality measures and patient survey data by gender for participating VAMCs
 
	Site-level formative feedback reports with comparisons to VISN and all participating VAMCs
Ongoing practice facilitation and expert review/feedback on local QI proposals and progress	
 
• Regular EBQI team contacts with local QI teams by telephone and email
 
• Troubleshooting of local problems using VISN oversight/communication plans
 
• Intermittent policy contacts (e.g., identify/disseminate key policy documents, obtain national guidance)
 
	Structured local QI project proposals (templated) Structured expert feedback (email and telephone summaries)
Facilitation or across-site collaboration and spread of effective QI innovations	EBQI team-moderated monthly calls with 1+ representative per intervention VAMC	Verbal summaries of local QI project progress (including shared materials across sites) Aggregated across-site formative feedback (from multiple data sources, e.g., patient surveys)
Technical work groups designed to provide additional evidence-based support in priority areas	VISN-level stakeholder panel meeting (above) used to also rate priority areas in which expert evidence-based consultation and support would be useful—work groups will be convened among national experts in clinical care and research in selected priority areas	Mini-systematic reviews in priority area(s) Practice scans of WH-PBRN site leads to identify best practices at other VAMCs

**Figure 3:** Evaluation components of the Women’s Health PACT trial.

Legend: PC, primary care; WH, women’s health; CATI, computer-assisted telephone interviews

